2.3. Exploratory Objectives

[figure not shown]
- a. Investigate the transmissibility of SARS-CoV-2 infection among household members.
- b. Investigate whether SARS-CoV-2 infection will be associated with more respiratory symptoms in children with asthma and other atopic conditions, as compared to children without asthma or other atopic conditions.
- c. Investigate whether SARS-CoV-2 infection will be associated with baseline nasal microbiome or with changes in the nasal microbiome and whether the underlying atopic status plays a role in this relationship.
- d. Investigate whether SARS-CoV-2 infection, as identified by the presence of virus in nasal secretions, will be associated with the presence of virus in stool.
- e. Determine whether IgA antibody specific for common coronaviruses (229E, OC43, NL63, HKU1) in the blood at baseline modifies the risk of SARS-CoV-2 infection or the severity of infection.
- f. Investigate earlier SARS-CoV-2 exposure by assaying historical samples from enrolled participants.
- g. Identify protective/risk factors for disease acquisition integrating all available data using machine learning approaches and network analysis to provide efficient representation of complex interactions.

3. Study Design

3.1. Description of Study Design

This is a prospective surveillance study in which subjects that are currently enrolled in NIH-funded studies (index participant) and their household contacts, including caregiver(s) and possibly a sibling, will be asked to enroll in the SARS-CoV-2 surveillance study. A minimum of 2 family members (index participant and a caregiver) and up to a maximum of 4 total members (additional caregiver and/or sibling) will be enrolled per family. The enrollment goal is approximately 2000 families. The enrollment period will be approximately 8 weeks, and each participant will participate for a minimum of 6 months with possible extension of the observation period. During the study, biological samples will be collected by the family at pre-determined intervals and symptom and exposure surveys will be completed remotely via a smart phone, on-line, or phone communications at the time the biological samples are collected (Figure 3.1 Study Overview). The Schedule of Events (Table A) provides more complete details of the study events and timing of these events. All biological samples (e.g. nasal swabs, peripheral blood, stool) will be collected by the caregiver at home using materials provided to the family. Peripheral blood will only be collected from participants 2 years of age and older. At the end of study, additional samples (e.g. nasal secretion and/or saliva samples) may be collected by the family or study staff at a site visit, if feasible.

If any member of the household develops symptoms compatible with COVID-19, the family will be instructed to complete a symptom survey for the affected household member. If completion of the symptom algorithm meets a study-specified threshold, this will be considered the first illness event for the family/household and an additional nasal swab will be collected from all study participants in the household and an additional stool sample (via swab) will be collected from the affected household member if they are a study participant. Blood will be collected from all study participants that are 2 years of age and older three weeks following this first illness event during the study period. Additional nasal swabs and stool samples will be collected from the index participants with every illness that meets the study-specified symptom threshold. For family members other than the index participant, additional samples associated with illnesses will be collected with the first illness event only.

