2.2. Secondary Objectives

- a. Determine SARS-CoV-2 antibody development in children and their household members.
- b. Compare SARS-CoV-2 infection status (detection of viral RNA in nasal secretions) and virus-specific antibody development for children with asthma and other atopic conditions (e.g. eczema) versus children without asthma or other atopic conditions.
- c. Determine mucosal immune responses to SARS-CoV-2 infection through gene expression profiling and examine whether these responses are influenced by the presence of asthma or other atopic condition.
- d. Determine whether topical, systemic, or inhaled steroids use, as directed by their care provider, modify the risk of SARS-CoV-2, the severity of infection, or expression of the SARS-CoV-2 receptor.
- e. Determine whether baseline demographic and environmental factors, such as age, sex, race, history of influenza vaccination, rural versus urban living, medications (such as ACE inhibitors), and smoking exposure modify the risk of SARS-CoV-2 infection or the severity of infection.

- f. Assess whether a history of RSV infection or bronchiolitis during infancy modifies severity of SARS-CoV-2 infection.

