3.3. Secondary Outcome(s)

- a. The percent of index participants and their household contacts with detectable SARS-CoV-2-specific antibodies in serum over the study period.
- b. The cumulative incidence of SARS-CoV-2 detection in nasal samples among index participants with asthma and other atopic disease over the study period as compared to index participants without any atopic disease.
- c. The percent of index participants with asthma and other atopic disease with detectable SARS-CoV-2-specific antibodies in serum over the study period as compared to index participants without any atopic disease.
- d. Changes in the nasal transcriptome that are associated with detection of SARS-CoV-2 in nasal samples among index participants and their household contacts over the study period.
- e. Changes in the nasal transcriptome that are associated with detection of SARS-CoV-2 in nasal samples among index participants with asthma and other atopic disease over the study period as compared to index participants without any atopic disease.
- f. Symptoms (including upper and lower airway, gastrointestinal, and systemic symptom as assessed via questionnaires) that are associated with detection of SARS-CoV-2 in nasal samples among index participants and their household contacts over the study period.
- g. The cumulative incidence of SARS-CoV-2 detection in nasal samples among index participants using topical, systemic, or inhaled steroids during the study period as compared to index participant that are not using topical, systemic, or inhaled steroids.
- h. The association of baseline demographic and environmental factors or history of bronchiolitis with the cumulative incidence of SARS-CoV-2 detection in nasal samples among index participants and their household contacts over the study period.

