4.3. Inclusion Criteria

Household members who meet all of the following criteria are eligible for enrollment as study participants:

- a. The index participant and/or caregiver understands the study procedures, is willing to conduct them at home, and has the ability to use either a computer or a smart phone to link to and respond to the study questionnaires. If the family does not have access to a computer or a smart phone, they are willing to speak with a study member to answer the questionnaires.
- b. The index participant is 21 years old and younger, lives with caregiver(s), and is or has been a participant in a NIH-funded clinical study from which information on respiratory conditions, including asthma, and other atopic and allergic diseases is available.
- c. The index participant and caregiver will reside in the United States, including Puerto Rico, for the duration of the study.
- d. The index participant will live with the caregiver for at least 50% of the time for the duration of the study.
- e. An English or Spanish speaker is available to serve as the primary contact and as the person who will be responsible for the completion of questionnaires and the collection of study biological samples.
- f. Qualifying siblings must be under 21 years of age and live in the same home as the index participant and caregiver.

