6.3. Unscheduled Assessments During Illness

6.3.1. First Illness. If any member of the household, including study participants and other people living in the same household that are not enrolled in the study, develop symptoms consistent with a viral illness, the caregiver will be instructed to fill in a symptom survey. If completion of the symptom survey meets a study-specified threshold in an illness algorithm, the caregiver will be instructed to collect, within 24 hours, unscheduled nasal swabs from all study participants and a stool sample from the affected participant. If the affected household member is not a study participant, she/he will be asked to enroll in the study only for this illness event and to provide a nasal swab and a stool sample. In addition, blood will be collected via a OnDemand device from all study participants that are 2 years old or older three weeks after the first illness event threshold is met. If the affected household member was not a study participant, she/he will also be asked to provide the 3-week blood sample. If the affected household member was not a study participant and refuses to register into the study or provide samples, then this illness event will not be recorded as the first illness event for the household.

6.3.2. Subsequent Illnesses. Subsequent illnesses will only be investigated if the index participant develops symptoms consistent with a viral illness that meet the same study-specific threshold as in the “first illness”. In such case, an extra nasal swab and a stool sample will be collected only from the index participant within 24 hours.

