11.1 Overview

A prospective longitudinal cohort of children and their families will allow us to estimate the incidence of SARS-CoV-2 infection and investigate the association of risks factors for infection while accounting for follow-up and censoring. This study will permit us to gain insights into the complex interaction of SARS-CoV-2 exposure, particularly within families, with participant sex, age, susceptibility, immunological profiles and clinical outcomes.

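### After a household's first illness only index participants get illness swabs, so 3.3h, if analysed on all swabs without regard to role, can show equal infection risk as an age difference

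*Combined protocol and SAP*

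**What the plan says.** Scheduled swabs are the same for everyone: every two weeks from Week 2 to Week 18, then Week 24 (section 6.2.1). Households that accept the extension add Weeks 20, 22, 26 and 28 (Table A, footnote 4).

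Illness swabs differ by role. Section 3.1: "Additional nasal swabs and stool samples will be collected from the index participants with every illness that meets the study-specified symptom threshold", whereas "For family members other than the index participant, additional samples associated with illnesses will be collected with the first illness event only". Section 6.3.1 has the caregiver "collect, within 24 hours, unscheduled nasal swabs from all study participants" at the household's first illness. Anyone living in the home can trigger that event, but an illness in a non-enrolled person who declines to join or to give samples does not use it up. For later illnesses, section 6.3.2 says "an extra nasal swab and a stool sample will be collected only from the index participant within 24 hours". Table A, footnote 2, agrees.

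Section 7 sends every swab to RT-qPCR. The only written event rule, in section 11.2 for the primary outcome, counts any positive nasal sample, whatever the reason for the swab.

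Outcome 3.3h concerns the association of baseline factors "with the cumulative incidence of SARS-CoV-2 detection in nasal samples among index participants and their household contacts over the study period". Objective 2.2e reads "Determine whether baseline demographic and environmental factors, such as age, sex, race, history of influenza vaccination". Section 4.3 says "The index participant is 21 years old and younger", and siblings must be under 21. Section 11.1 undertakes to "investigate the association of risks factors for infection while accounting for follow-up and censoring". Section 11.2 gives no model for 3.3b, 3.3g or 3.3h. Its one regression is a Cox model for time to detectable antibody.

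**The concern.** Once a household has used its first illness event, an infected index child with symptoms is swabbed and an infected caregiver with the same symptoms is not, unless a scheduled swab happens to fall in the RNA-positive window. Because everyone over 21 follows the contact rule, an age contrast in 3.3h partly compares two testing rules. Allowing for follow-up and censoring does not remove this, because both people are under observation throughout.

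Outcomes 3.3b (atopy) and 3.3g (steroid use) compare index participants with each other, so the role rule cannot act there. Extra swabs still follow symptoms. Section 1 cites greater susceptibility to respiratory viruses in atopic children, and exploratory objective 2.3b asks whether they have more respiratory symptoms once infected. If one group reaches the threshold more often, more of its infections are found.

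At stake is whether an age effect (objective 2.2e) or a protective effect of allergic airway disease (raised in section 1) can be told apart from testing frequency.

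**Working it through.** The plan gives no detection figure to reproduce. Its only figures, the Wilson intervals in section 11.3 for n = 2000, reproduce to rounding (3%: 2.34 to 3.84) except the lower limit at 10% (8.76 against 8.7), which does not matter here.

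**Assumptions, none in the documents.** RNA is detectable for D = 7 / 10 / 14 days. A share t of infections reaches the threshold, and c = 0.8 of those are swabbed. A household has L other threshold illnesses in 24 weeks, spread evenly. A share a of scheduled swabs is done. True infection risk is equal unless stated.

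**Step 1, continuous 2-weekly swabs (the extension pattern).** Scheduled detection is d = a × min(1, D/14). The share of infections falling after the household's first illness is f = 1 − (1 − e^−L)/L, which is 0.368, 0.568 and 0.755 for L = 1, 2, 4. Index detection = 1 − (1 − d)(1 − ct). Contact detection = 1 − (1 − d)(1 − ct(1 − f)). With t = 0.5, ct = 0.4. With L = 2, ct(1 − f) = 0.173. For a = 1:

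| D (days) | d | Index | Contact | Ratio |
|---|---|---|---|---|
| 7 | 0.500 | 0.700 | 0.586 | 1.19 |
| 10 | 0.714 | 0.829 | 0.764 | 1.08 |
| 14 | 1.000 | 1.000 | 1.000 | 1.00 |

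With a = 0.8 the ratios are 1.27 / 1.15 / 1.05.

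**Step 2, base 24-week schedule.** Ten swabs in 168 days, with none between Weeks 18 and 24, give d = 10D/168 = 0.417 / 0.595 / 0.833 for a = 1. An infection at week t* that the schedule misses is caught in a contact with probability 0.4 × e^(−2t*/24). Averaging over t*, index against contact is 0.650 against 0.513, 0.757 against 0.656, and 0.900 against 0.846. The ratios are 1.27 / 1.15 / 1.06. The gap matters because it falls late, when most households have used their first event.

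A separate simulation of this schedule, with every threshold illness swabbed and half of households past their first event by Week 12, gives 0.797 against 0.694 (1.15) at 10 days. Over windows of 7 to 21 days, 20 to 80% reaching the threshold and 25 to 75% of households past the first event by Week 12, it gives 1.01 to 1.56.

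**Step 3, what a test would do.** Take 2000 index participants and 2000 caregivers, 10% true incidence in both, and D = 10. Observed incidence is 7.57% against 6.56%. The pooled standard error is √(2 × 0.0707 × 0.9293/2000) = 0.0081, so the expected z is 0.0101/0.0081 ≈ 1.24. A nominal 5% test rejects about 24% of the time, treating members of a family as independent.

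**Step 4, children less often symptomatic.** With t = 0.3 for index and 0.6 for contacts, continuous swabs, a = 1 and D = 7 / 10 / 14, the ratio is 0.95 / 0.98 / 1.00 (L = 1), 1.03 / 1.01 / 1.00 (L = 2) and 1.11 / 1.05 / 1.00 (L = 4).

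**Step 5, outcome 3.3b.** Ratio = [d + (1 − d)c·tA]/[d + (1 − d)c·tN], where A is atopic and N non-atopic. Equal t gives 1.00. For a true ratio of 0.80 on continuous swabs:

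| tA vs tN | a = 1 | a = 0.8 |
|---|---|---|
| 60% vs 30% | 0.95 / 0.87 / 0.80 | 1.01 / 0.92 / 0.85 |
| 30% vs 60% | 0.67 / 0.74 / 0.80 | 0.63 / 0.69 / 0.76 |

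The ends come from d = 0.4: 0.688/0.544 = 1.265, and 0.8 × 1.265 = 1.01, while 0.8/1.265 = 0.63.

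**Step 6, is scheduled-only always safer?** No. With L = 2, t = 0.5 and a = 1, if RNA lasts 7 days in children and 10 in adults, scheduled-only gives 0.500/0.714 = 0.70 and all swabs give 0.700/0.764 = 0.92, for a true 1.00.

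**The case against.** Several points on the other side stand.

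- A reader might infer that nothing in the plan is free of the swab rule. That is not so. Outcome 3.3c compares antibody by atopy, and the Cox model in section 11.2 relates demographic and clinical factors to antibody in index participants and household members. End-of-study blood does not depend on symptoms or role, and blood three weeks after the first illness is taken from all participants, in each case at age 2 and over. These are largely swab-independent checks. Their limits are that section 7 says no optimal assay had been identified, and that the plan does not link them to 3.3b or 3.3h.
- Outcome 3.3h does not itself set index against contacts, its model is unspecified, and the event rule is written for the primary outcome. Adjustment for role is therefore left open, not excluded, and applying the event rule to 3.3h is an inference.
- Equal symptom rates may not be the likeliest case. Section 1 notes that many confirmed paediatric cases are asymptomatic, and Step 4 is then near 1. The documents do not support a claim that detection in children is inflated, only that it can be.
- A within-role age contrast is not clean either. Section 5.1.1 changes the swab site at age 11. If 30% of sibling and 60% of caregiver infections reach the threshold, that contrast reads 0.91 / 0.96 / 1.00 for a true 1.00 (L = 2, continuous swabs).

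A reader might also infer that extra index swabs over-count the primary outcome. They do not: an illness swab finds an infection that is present, and dropping such swabs would miss cases.

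**Conclusion.** The concern holds as a statement of what can happen. The difference in swab rules is certain from the text, as is the absence of any stated handling of it in 3.3h. Its size rests on assumed RNA duration, symptom rates, illness frequency and adherence. With equal symptom rates and L = 2 it ranges from nil (14 days, complete continuous swabs) to about 1.27 (7 days, 24-week schedule, all swabs done). With fewer symptoms in children it is 0.95 to 1.11 on continuous swabs, so the direction is not settled.

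For 3.3b the problem is conditional on a difference in reaching the threshold. Under 60% against 30%, or the reverse, a true ratio of 0.80 could read anywhere from 0.63 to 1.01 on continuous swabs. The same reasoning applies to 3.3g. This is an inexpensive improvement to secondary analyses and no criticism of the primary outcome or of the sampling scheme.

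**What to change.** - Keep all swabs for the primary outcome.
- Record each swab's reason: scheduled, own illness, or another member's illness.
- In 3.3h, include role in the model or stratify by it, and report age effects within role. Note that swab site also changes at age 11 and that symptom differences may remain.
- For 3.3h, 3.3b and 3.3g, add a sensitivity analysis in which the event is the first positive scheduled swab. Report by group the swabs per person and the detections found only on illness swabs.
- Read these results alongside the planned antibody analyses. If the versions disagree, state that unequal testing is not excluded.

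The cost is analysis-plan wording and one derived field, since role is already known. The scheduled-only version loses events, by 1 − d/(mean all-swab detection of the two groups). On continuous swabs with L = 2, the index-contact comparison loses 22 / 10 / 0% with all swabs done and 30 / 18 / 7% with 80% done. For 3.3b at 60% against 30%, the loss is 26 / 13 / 0% and 35 / 21 / 8%. The base schedule loses more: at 7 days with all swabs done, 1 − 0.417/0.5815 = 28% in the index-contact comparison. Scheduled-only is not always nearer the truth (Step 6), so neither version should be declared correct. Within-role contrasts have fewer people, because a sibling is optional and the number is not given.

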3.2. Primary Outcome

The cumulative incidence of SARS-CoV-2 RNA detection in nasal samples among index participants and their household contacts over the study period.

3.3. Secondary Outcome(s)

- a. The percent of index participants and their household contacts with detectable SARS-CoV-2-specific antibodies in serum over the study period.
- b. The cumulative incidence of SARS-CoV-2 detection in nasal samples among index participants with asthma and other atopic disease over the study period as compared to index participants without any atopic disease.
- c. The percent of index participants with asthma and other atopic disease with detectable SARS-CoV-2-specific antibodies in serum over the study period as compared to index participants without any atopic disease.
- d. Changes in the nasal transcriptome that are associated with detection of SARS-CoV-2 in nasal samples among index participants and their household contacts over the study period.
- e. Changes in the nasal transcriptome that are associated with detection of SARS-CoV-2 in nasal samples among index participants with asthma and other atopic disease over the study period as compared to index participants without any atopic disease.
- f. Symptoms (including upper and lower airway, gastrointestinal, and systemic symptom as assessed via questionnaires) that are associated with detection of SARS-CoV-2 in nasal samples among index participants and their household contacts over the study period.
- g. The cumulative incidence of SARS-CoV-2 detection in nasal samples among index participants using topical, systemic, or inhaled steroids during the study period as compared to index participant that are not using topical, systemic, or inhaled steroids.
- h. The association of baseline demographic and environmental factors or history of bronchiolitis with the cumulative incidence of SARS-CoV-2 detection in nasal samples among index participants and their household contacts over the study period.

3.4. Exploratory Outcome(s)

- a. Symptoms associated with detection of SARS-CoV-2 in nasal samples.
- b. Nasal microbiome outcomes of alpha and beta diversity among index participants and their household contacts with detectable SARS-CoV-2 in nasal samples over the study period.
- c. The percent of participants with symptomatic SARS-CoV-2 infection in whom the virus can be detected in stool.
- d. Levels of IgA antibodies specific for common coronaviruses (229E, OC43, NL63, HKU1) in the blood at baseline.
- e. The percent of index participants with detectable SARS-CoV-2-specific antibodies in samples that were collected and stored prior to the current study period.

3.5 Randomization

N/A

4. Selection of Participants and Clinical Sites/Laboratories

4.2. Rationale for Study Population

The study population will include index participants and their families. The intent is to recruit index participants who have asthma and/or other atopic or allergic conditions, as well as healthy index participants, with extensive medical information and information on atopic and allergic status available as a result of their participation in the NIH-funded research study. As many of these studies are birth cohort studies, there is also extensive information on the parents. Furthermore, most of these families have experience with collection of respiratory samples and are familiar with respiratory questionnaires.

